4.2. Exclusion Criteria

- (1) Receipt of chemotherapy, immunotherapy, cryotherapy, radiotherapy, or anti-androgen therapy other than LMIS 50 mg under Protocol FP01C-13-001 for treatment of carcinoma of the prostate during the subject's participation in Protocol FP01C-13-001. Radiation for pain control will be allowed during the study.
- (2) Receipt of any LHRH suppressive therapy within 6 months of Screening Visit OTHER THAN LMIS 50 mg under Protocol FP01C-13-001
- (3) Subject has used prohibited treatments as listed in the Section 8.2 during participation in Protocol FP01C-13-001.
- (4) Any pathological event, clinical adverse event, or any change in the subject's status at the end of FP01C-13-001 giving indication to the investigator that further participation in the study may not be the best interest of the subject
- (5) Investigator considers that it is no longer feasible for the subject to be included in a study of LMIS 50 mg
- (6) Subjects with persistent, non-castrate testosterone levels judged by the investigator
- (7) Uncontrolled intercurrent illness that would jeopardize the subject's safety, interfere with the objectives of the protocol, or limit the subject's compliance with study requirements, as determined by the Investigator in consultation with the Sponsor

4.3. Withdrawal criteria

Discontinuation from study is defined as discontinuation of all study visits and examinations. Participants may voluntarily withdraw from the study for any reason at any time. They may be considered withdrawn if they state an intention to withdraw, or fail to return for visits, or become lost to follow up for any other reason.

Study period:

Generally, subjects will be withdrawn from the study if any of the following occurs during the study period, i.e. from Screening Visit to end of study (EOS):

- (1) Screening failure
- (2) Lost to follow-up
- (3) Subject who decides to withdraw their informed consent
- (4) Subject has used prohibited treatments as listed in the Section 8.2.
- (5) Any pathological event, clinical adverse event, or any change in the subject's

status giving indication to the investigator that further participation in the study may not be the best interest of the subject

- (6) Investigator considers that it is no longer feasible for the subject to be included in the study
- (7) Subjects with persistent, non-castrate testosterone levels judged by the investigator

Subjects who are withdrawn due to adverse event(s) or serious adverse event(s) should be followed until resolution or until the event is considered stable.

5. Study Treatment

5.1. Treatment plan summary

Subjects enrolled in this open-label, phase IIIb safety extension study will receive a single subcutaneous injection of LMIS 50mg every 6 months for up to 2 doses.

5.2. Treatment assignment

Subjects will be assigned the SAME SCREENING and RANDOMIZATION NUMBER(s) as was assigned to that individual subject under Protocol FP1C-13-001.

The randomization number should be recorded on the CRF.

5.3. Description of study drug

Leuprolide is a synthetic nonapeptide analog and agonist of the naturally occurring LH-RH or GnRH receptor. Leuprolide is a more potent agonist of the GnRH receptors relative to the natural GnRH peptide due to its increased affinity for the GnRH receptors and longer half-life. As a GnRH agonist, leuprolide functions as an inhibitor of gonadotropin secretion when administered continuously in therapeutic doses. Leuprolide acetate was introduced in 1985 for the treatment of prostate cancer as an alternative to surgical castration and estrogen therapy (NDA 19-010). Subjects with prostate carcinoma tend to accept this palliative treatment because its effects on gonadotropin are reversible when treatment is discontinued.

LMIS 50 mg is prefilled and supplied in a ready-to-use sterile syringe for subcutaneous injection. It contains 50 mg leuprolide mesylate [REDACTED] in a [REDACTED] formulation dissolved in a [REDACTED].

Investigational product dose administration procedures are outlined in the Investigational Product Instruction Manual.

5.4. Rationale for dose

The LMIS 50 mg dosage form has been developed to deliver bioactive leuprolide over a 6 month period after subcutaneous administration with a release profile similar to that of the Eligard® 45 mg formulation. The LMIS 50 mg dosage and its use as a sustained-release or depotdosage form have shown to be both efficacious and safe in similar leuprolide products (i.e. Eligard® 45 mg).

5.5. Warning and Precautions

Leuprolide acetate has the following established significant adverse events:

- Clinical testosterone flare reaction in men with prostate cancer

- Osteoporosis

Like other LH-RH analogs, leuprolide acetate causes a transient increase in the serum concentration of testosterone during the first week of treatment. This effect may cause subjects to experience a worsening of symptoms or an onset of new symptoms including bone pain, neuropathy, hematuria, or ureteral or bladder outlet obstruction. Long-term use of an LHRH agonist has been reported to decrease bone mineral density which can increase the risk of osteoporosis and skeletal bone fractures.

Other reported adverse events of leuprolide acetate include hypogonadism, reduction in glucose tolerance, anemia, and prolongation of the QT/QTc interval.

5.6. Packaging and labeling

LMIS 50 mg will be provided to the Investigator in a single use kit by Foresee Pharmaceuticals Co. Ltd. (previously as Foreseeacer Pharmaceuticals, Inc.), or its designee. The kit is packaged in a carton box and consists of a prefilled ready-to-use 1-mL sterile syringe, a sterile needle, and a silicone desiccant pouch to control moisture uptake. The prefilled syringes containing LMIS 50 mg (study drug) and the carton boxes in which the syringes are packaged both are labeled with a kit number. Each site will be provided with emergency back-up kits of study drug in case of contamination; the investigational sites will be directed to assign specific emergency kits to individual subjects by matching the subject's code to the kit label.

All study drug is minimally labeled with the information below; however, any additional information appearing on the label will conform to local regulatory requirements.

- Product name
- Batch number
- Protocol number
- Kit number
- Storage instructions
- Sponsor address
- Expire date
- “Clinical trial use only”

The details noted on the labels are in accordance with applicable regulatory requirements.

It is important to note that subjects may be dosed under this protocol and followed for safety information up to the date of expiry of the clinical trial material (CTM) for this study. The date of expiry of the current CTM batch# CL0080 is May 31, 2016. Foresee expects to be able to extend the date of expiry to Nov 30, 2016 based on ongoing stability study. However, there is no guarantee that the expiry dating period can be successfully extended.

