1.3. Study rationale

At the time of the initiation of this study, Foresee is conducting Protocol FP01C-13-001, entitled, "An Open-Label, Single-Arm Study of the Safety, Efficacy, and Pharmacokinetic Behavior of Leuprolide Mesylate for Injectable Suspension

(LMIS 50 mg) in Subjects with Advanced Prostate Carcinoma." In that protocol, it outlines that for subjects that complete 12 months of treatment with LMIS 50 mg and remain eligible for continued androgen deprivation therapy with LMIS 50 mg, the subject could receive up to 12 months of additional therapy with LMIS 50 mg. Protocol FP01C-13-001-EX represents the up to 12 months of additional therapy after completion of 12 months of treatment with LMIS 50 mg under Protocol FP01C-13-001.

It is important to note that subjects may be dosed under this protocol and followed for safety information up to the date of expiry of the clinical trial material (CTM) for this study. The date of expiry of the current CTM batch# CL0080 is May 31, 2016. Foresee expects to be able to extend the date of expiry to Nov 30, 2016 based on ongoing stability study. However, there is no guarantee that the expiry dating period can be successfully extended.

2. Study Objective and Endpoints

This is a safety extension of up to 12 months of additional treatment with LMIS 50 mg after the subject has completed 12 months of treatment under Protocol FP01C-13-001 and remain eligible for continued treatment with androgen deprivation therapy. Subjects participating in Protocol FP01C-13-001-EX will be followed for safety only.

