6.5. Day 252±7 days

- (1) Conducted physical examinations and record vital signs
- (2) Collect fasting blood sample for analysis of:
 - Hematology: CBC, including Hb, Hct, RBC count, WBC count, WBC differential and platelet count
 - Biochemistry: ALT, AST, ALP, total bilirubin, BUN, Serum Cr, electrolytes (K, Na, Mg, Ca and P), blood glucose, lipid profile (LDL, HDL, triglycerides)
 - PSA level
- (3) Collect urine sample for urinalysis test:
 - pH, specific gravity, leukocyte, erythrocyte, protein
- (4) Record concomitant medication(s)
- (5) Record AE(s)

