6.6. Day 336±7 days (End of Study / Early Termination)

- (1) Conduct physical examination and record vital signs
- (2) Perform 12-lead ECG (5 minute supine)
- (3) Collect fasting blood sample for analysis of:
 - Hematology: CBC, such as Hb, Hct, RBC count, WBC count, WBC differential

and platelet count

- Biochemistry: ALT, AST, ALP, total bilirubin, BUN, Serum Cr, electrolytes (K, Na, Mg, Ca and P), blood glucose, lipid profile (LDL, HDL, triglycerides)
- HgbA1c
- PSA level

(4) Collect urine sample for urinalysis:

- pH, specific gravity, leukocyte, erythrocyte, protein

(5) Record concomitant medication(s)

(6) Record AE(s)

(7) Exit off the study

(8) For early termination subjects, phone contacts should be performed at 3 and 6 months after the last injection of study drug to collect drug-related AE, concomitant medication or non-drug therapy received for AE treatment, disease progression status, and subject survival status

7. Study Assessments

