7.2.2. Hematological / Biochemistry Examinations

Fasting blood samples will be collected for hematological, biochemistry and biological examinations.

Hematological tests will include complete blood count (CBC), including hemoglobin (Hb), hematocrit (Hct), red blood cells (RBC), white blood cells (WBC), WBC differential (neutrophils, eosinophils, basophils, lymphocytes and monocytes) platelet counts and HgbA1c. Biochemistry tests will include ALT, AST, ALP, total bilirubin, BUN, Serum Cr, electrolytes (K, Na, Mg, Ca and P), blood glucose and lipid profile (LDL, HDL, triglycerides).

Laboratory tests, except for the HgbA1c, will be performed during the Screening Visit and at Day 84 ±7 days, Day 168±7 days, Day 252 ±7 days and Day 336±7 days. The HgbA1c will be performed at the final visit (Day 336 or End of Study Visit).

PSA will be performed at Day 84±7 days, Day 168±7 days (prior to dosing), Day 252±7 days, and at the final visit (Day 336±7 days or End of Study Visit).

The End of Study laboratory tests, HgbA1c and PSA assessments for Protocol FP01C-13-001 will be used as the Baseline assessment for this study.

Blood samples for laboratory tests will be collected in the hospital or at the investigative site and will be sent to the Central Laboratory for analyses.

*If the patient completed 12 months of treatment with LMIS 50 mg more than 28 days prior to entering the Extension study, the testosterone level should be repeated and the repeat test should indicate that the patient maintains a castrate-level of testosterone. In addition, the ECOG, PE, ECG, laboratory and PSA tests should be repeated.

If the patient has completed 12 months of treatment with LMIS 50 mg under Protocol FP01C-13-001 within the last 28 days, they will be allowed to enter the Extension study without repeating the testosterone measurements, ECG, PE, laboratory and the PSA tests.

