10.3. Safety analysis

The transition matrix will be summarized for the following:

- Change from baseline in vital signs (BP, HR, RR)
- Change from baseline in physical examinations (including weight)

The summary results of vital signs (BP, HR, RR) and weight at Baseline, End of Study Visit, and the change from baseline will be summarized descriptively. Also the change from baseline to the End of Study Visit will be tested by paired t-test or Wilcoxon

signed-rank test at a significance level of 0.05.

The transition matrix of physical examination will be summarized.

- Change in laboratory data, including liver function (AST, ALT, ALP), renal function (BUN, Serum Cr), complete blood count with platelets, clinical chemistries (K, Na, Mg, Ca and P), urinalysis, serum glucose, and lipid profile (LDL, HDL, triglycerides) and HgbA1c

The summary results of laboratory data at the Baseline and the End of Study Visit, and change from baseline to End of Study Visit will be summarized by descriptive statistics and paired t-test or Wilcoxon signed- rank test will be used at a significance level of 0.05.

- Adverse event (AE) reporting

The analysis of adverse events will be tabulated by system organ class (SOC) and preferred terms according to the current MedDRA dictionary. Preferred terms will be used and presented as standardized tabulations by frequency and incidence rates. Adverse event incidence rates will be analyzed by severity and relationship to study drug. Any adverse event leading to death, discontinuation from the study, or change of dose will be listed as per regulation.

If any serious adverse event occurs, a brief summary about the serious adverse event will be described and listed.

- Change in 12-lead resting electrocardiograms (ECGs)

The summary results of 12-lead resting ECG at Baseline and the End of Study Visit will be summarized descriptively. The transition matrix for ECGs will be summarized.

11. Study Administrative Structure

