1. INTRODUCTION

This is a multi-center, open-label, single-arm safety extension study. All subjects will be males with advanced prostate carcinoma that have completed 12 months of therapy with LMIS 50 mg under Protocol FP01C-13-001, judged by investigators to be candidates for continued medical androgen ablation therapy, and all subjects will continue to receive LMIS 50 mg.

This statistical analysis plan (SAP) is based on protocol version 1.0, dated 01Oct2015. The SAP provides details of data handling procedures and statistical analysis methods for safety evaluations. It also outlines statistical programming specifications for tables, listings and figures, and other details on the analyses not provided in the study protocol.

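### The rule tying safety follow-up to drug-batch expiry is not reconciled with the Day 252 and Day 336 visits, and the calls to early terminators ask only for drug-related AEs

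*Protocol*

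**What the plan says.** **Expiry.** Protocol 5.6, in a paragraph that also stands in 1.3, says that "subjects may be dosed under this protocol and followed for safety information up to the date of expiry of the clinical trial material (CTM". One limit covers both dosing and follow-up. The confirmed date is given next: "The date of expiry of the current CTM batch# CL0080 is May 31, 2016". The sponsor expects to extend it to 30 Nov 2016, but "there is no guarantee that the expiry dating period can be successfully extended".

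**Visits.** The last two safety visits are headed "6.5. Day 252±7 days" and "6.6. Day 336±7 days (End of Study / Early Termination". They also appear in Table 1 and in SAP 3.4. None of these places mentions expiry. Two things depend on the last visit:

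- For glycated haemoglobin, "The HgbA1c will be performed at the final visit (Day 336 or End of Study Visit". It is the only post-baseline measurement.
- For vital signs and weight, Protocol 10.3 says "Also the change from baseline to the End of Study Visit will be tested by paired t-test" or by a signed-rank test. Laboratory changes are treated in the same way.

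**Early-termination calls.** Subjects who stop early are to be telephoned 3 and 6 months after their last injection. All seven descriptions of these calls limit the AEs collected to drug-related ones: synopsis VIII, synopsis schedule footnote 4, Protocol 3.1, Table 1 footnote 4, Protocol 6.6, SAP 3.1 and SAP 3.4 footnote 4. SAP 10.1 has every AE recorded whatever its relationship to treatment, including after dosing. It closes the Newly TEAE window when the subject is off study, without tying that term to a particular visit or call.

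**The concern.** Every endpoint of this extension is a safety endpoint, so the length and completeness of follow-up is its main product. A site that takes the expiry sentence at its word could stop observing a dosed subject before Day 336 falls due. The protocol's final-visit tests and the one post-baseline glycated haemoglobin would then rest on earlier data or on none.

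The call wording raises a related problem. The synopsis describes the product as releasing drug over 6 months. A subject who completes has all AEs recorded through the 168 days from the Day 168 visit to Day 336. A subject who stops early has new events after the termination visit collected by call only if they are judged drug-related, and the study is open-label. Collection then depends on the causality judgement that the AE tables are meant to report.

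**Working it through.** Neither document states a maximum study day, so there is no plan figure to reproduce. The check is calendar subtraction.

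**Inputs**

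- Expiry: 31 May 2016 confirmed, 30 Nov 2016 hoped for (Protocol 1.3, 5.6).
- Earliest Day 0: 01 Oct 2015. This is an assumption, because no first-dose date is given. It is the protocol date: "This statistical analysis plan (SAP) is based on protocol version 1.0, dated 01Oct2015". An earlier start is unlikely, and a later one shortens follow-up.
- Visit windows of 7 days either way: Day 252 opens at 252 − 7 = 245, and Day 336 at 336 − 7 = 329 (Protocol 6.5, 6.6).

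**Latest study day on a literal reading** = expiry date − Day 0

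| Day 0 | Expiry 31 May 2016 | Expiry 30 Nov 2016 |
|---|---|---|
| 01 Oct 2015 | 243 | 426 |
| 01 Nov 2015 | 212 | 395 |
| 01 Dec 2015 | 182 | 365 |
| 01 Feb 2016 | 120 | 303 |

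**Confirmed expiry**

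- Day 252 is missed by 252 − 243 = 9 days, or 245 − 243 = 2 with the window.
- Day 336 is missed by 336 − 243 = 93 days, or 329 − 243 = 86 with the window.
- Day 168 falls by expiry only for Day 0 by 31 May 2016 − 168 days = 15 Dec 2015 (22 Dec 2015 if held on Day 161).
- Follow-up after a Day 168 injection is at most 243 − 168 = 75 days, and 75/168 = 45% of the scheduled 168. If given on Day 161, it is 243 − 161 = 82 days, and 82/168 = 49%.
- If the sentence also governs the calls, they do not fill this gap. After a second injection on the earliest Day 168 (17 Mar 2016), they fall on 17 Jun and 17 Sep 2016, which is 17 and 109 days after expiry.

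**Extended expiry**

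- Day 336 is reached for Day 0 by 30 Nov 2016 − 336 days = 30 Dec 2015 (06 Jan 2016 with the window).
- Day 252 is reached for Day 0 by 23 Mar 2016 (30 Mar 2016 with the window).

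**The calls: which rules apply?** No arithmetic settles this, so the passages are compared.

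- Pointing to calls after study exit: Protocol 4.3 ends the study period at EOS. Protocol 6.6 puts exit from the study at step 7 and the calls at step 8. Protocol 18 treats the study as complete at the early-termination visit.
- Pointing to calls within the study: Protocol 3.1 and SAP 3.1 make them part of the design, and Protocol 9.1 includes telephone follow-up during the study when AEs are sought.
- SAP 10.1's recording sentence has no end point after dosing, so it conflicts with related-only collection on either reading. Listing 16.2.13 does not help, because its AE field only checks completeness.

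**Effect of including call-reported AEs.** Six months after a Day 168 injection is about 168 + 183 = Day 351, or 351 − 336 = 15 days beyond a completer's last visit.

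**The case against.** The expiry sentence says may, and its purpose could be to limit dosing only. The objective promises no more than up to 1 year, and the supply limit is disclosed openly. The SAP schedules and tabulates Day 336 and has no expiry-related withdrawal reason apart from Other, so it appears to expect full follow-up. Protocol section 6 sends anyone who withdraws early to the final-visit assessments, so an early-termination visit before expiry could supply final data, including glycated haemoglobin. The SAP also analyses change to Day 168 for laboratory values, vital signs and ECG. All of this stands.

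A reader might infer that follow-up stops at Day 243 for everyone. The documents do not support that. Day 243 needs both an unextended expiry and dosing on the protocol date. The limit named is expiry of the trial material for the study, and 31 May 2016 is the date of the current batch.

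On the calls, a reader might infer a flat contradiction with Protocol 9.1. That also goes too far, because its telephone follow-up is confined to the study, and 4.3, 6.6 and 18 can be read as placing the calls after exit. Related-only collection would then be a deliberate choice. What remains is the conflict with SAP 10.1 and the unequal AE collection between early terminators and completers.

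**Conclusion.** The concern holds as a failure to reconcile passages. It is not evidence that follow-up was cut or that events were missed.

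On a literal reading, with no Day 0 before 01 Oct 2015 and the confirmed expiry, no subject reaches the Day 252 or Day 336 window. With the hoped-for extension, subjects whose Day 0 falls after 30 Dec 2015 (06 Jan 2016 with the window) still do not reach Day 336 by expiry. How many subjects this would affect cannot be worked out, because dosing dates are not given.

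The gap in the calls is narrow: new events after the termination visit that the investigator judges unrelated. AEs already open are followed, and Protocol 9.3 requires prompt reporting of fatal or life-threatening events during the study whatever their cause. The documents give no number of early terminators or of unrelated AEs, so no count of missed events can be stated. The point is still worth acting on, because events never asked about at a call may not be recoverable later.

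**What to change.** 1. Reconcile Protocol 1.3 and 5.6 with the visit schedule, so that the expiry date is not read as ending the scheduled safety visits or calls for subjects already dosed. This changes nothing about dosing.
2. In all seven places listed above, word the early-termination calls as collecting all AEs and SAEs, related or not.
3. As a consequence, state in SAP 10.1 whether call-reported AEs enter the Newly TEAE tables, and flag them so that events after Day 336 can be shown separately from the period that completers share.

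The cost is wording in both documents, a wider script for calls already planned and one flag variable. No visits or contacts are added beyond those already planned. Recorded AE counts will rise slightly, mostly through events judged unrelated.

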5.7. Supply, Delivery, Storage of Study Drug

LMIS 50mg is supplied by Foresee Pharmaceuticals Co. Ltd. (previously as Foreseeacer Pharmaceuticals, Inc.) The Investigational Product (IP) will be managed and stored safely and properly in a secured, lockable area by a designated, qualified person at the investigative site.

The IP will be shipped to the study site by a contracted delivery agent. The representative PI of the site will be in charge of the management and dispensation of the IP. Shipping receipts from receipt of IP or shipment of IP should be retained by the investigational site as part of the study records.

The LMIS 50mg must be stored under refrigeration at 2 - 8°C.

